### 11.23 Polymorphism analysis

The presence or absence of the polymorphisms detected will be compared to 5HT1A receptor PET binding and seizure frequency outcome in an exploratory manner.

### 11.3 Safety Analysis

Adverse events will be recorded at each clinic visit or more frequently as reported by patients. Safety data (adverse events, vital signs, laboratory tests and physical examination) will be subject to clinical review and summarized by appropriate descriptive statistics.

### 11.4 Sample size and power calculation

We assume that the mean difference between drug and placebo will be a 15% lower seizure rate, (representing a 30% improvement on drug versus 15% improvement on placebo versus baseline), and that the standard deviation of difference is 22%.

Based on a paired t-test, the estimated sample size is 19 to obtain 80% power at a significance level of 0.05. In order to balance the two arms we will accrue patients until 20 completers have been obtained. We request a total of 30 subjects to take into account a possible 20% dropouts.

Paired t-test of mean difference equal to zero

	1	2	3	4
Test significance level, $\alpha$	0.050	0.050	0.050	0.050
1 or 2 sided test?	2	2	2	2
First condition mean, $\mu_1$	30.000	30.000	30.000	30.000

Second condition mean, $\mu_2$	15.000	15.000	15.000	15.000
Mean difference, $\mu_d = \mu_1 - \mu_2$	15.000	15.000	15.000	15.000
Standard deviation of differences, $\sigma_d$	22.000	23.000	20.000	25.000
Effect size, $\omega =  \mu_d  / \sigma_d$	0.682	0.652	0.750	0.600
Power ( % )	80	80	80	80
n	19	21	16	24

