## 7.4 Study design

Following screening and a baseline phase (up to 6 weeks), patients will enter a treatment phase of 2 periods (Period 1 and Period 2) with a washout phase between periods 1 and 2. If patients have 4 seizures in less than six weeks during the baseline phase, they do not need to wait the entire 6-weeks to begin the treatment phase (Period 1) of the study. Each treatment period will last approximately 12-16 weeks. Following Period 1, there will be a wash-out of 4 – 6 weeks where no study medication will be taken. During each treatment period, there will be two Clinical Center visits. The first visit will entail clinical assessments and will occur 6-week +/- 2 weeks after starting the study drug and the second visit will entail clinical assessments and neuropsychological and mood assessment and will occur at the end of each maximum tolerated dose (MTD) treatment period. In addition, a follow-up visit will occur approximately one month following the end of the second treatment period that will include a physical examination and review of any adverse events. The total duration of the study is 42-46 weeks (+/- 4 weeks). Each clinic visit will last approximately one hour. The neuropsychological and mood evaluation at the end of each treatment period will last up to three hours.

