#### 7.52 Randomization to Active drug or Placebo

Subjects will be randomized at the end of baseline to either active drug or placebo using a 1:1 ratio per the randomization schedule. The randomization schedule will be generated, secured, distributed, and stored by the NIH Pharmacy. Patients may be outpatients or inpatients during titration depending on their geographical location, need for additional education on the titration process or if they are participating in concurrent studies with the Clinical Epilepsy Section. All patients will be given an exact written titration schedule to follow.

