## 11. Statistical Analysis

### 11.1 Analysis of Primary Endpoint

Analysis of variance will be used to test for a treatment order effect. A carry-over effect is unlikely due to the long washout period. A paired samples Student's T-test will then be used to compare seizure frequencies during placebo and active treatment periods (see sample size calculation below). If the carry-over effect is significant, a two group T-test will be applied separately for each period.

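### The primary paired t-test has no period term, so a change in seizure rate between the two periods costs power and, if completers split unequally by sequence, shifts the drug estimate

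*Combined protocol and SAP*

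**What the plan says.** Section 7.52 sets the allocation: "Subjects will be randomized at the end of baseline to either active drug or placebo using a 1:1 ratio per the randomization schedule". It mentions neither blocking nor replacement of dropouts within a sequence. The schedule is held by the pharmacy and is not part of the documents.

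Section 7.4 gives treatment periods of about 12 to 16 weeks, separated by a break: "Following Period 1, there will be a wash-out of 4 – 6 weeks where no study medication will be taken".

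Section 11.4 sizes the trial: "Based on a paired t-test, the estimated sample size is 19 to obtain 80% power at a significance level of 0.05". It then goes from 19 to 20: "In order to balance the two arms we will accrue patients until 20 completers have been obtained". That is a total. No target per sequence is given.

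Section 11.1 begins with an analysis of variance that tests for a treatment order effect. The primary comparison follows: "A paired samples Student's T-test will then be used to compare seizure frequencies during placebo and active treatment periods". The only stated consequence of the first step is a separate two-group t-test in each period if carry-over is significant. Nothing is said about what happens if the periods differ without carry-over.

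**The concern.** In a two-period crossover, a patient's active-minus-placebo difference contains the drug effect and also any change in seizure rate between the periods. That change enters with one sign in patients who take active drug first and with the opposite sign in the others. A paired t-test pools all differences as one sample, so it cannot separate the two.

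There are two consequences. With equal sequences the opposite signs cancel in the mean, but they spread the differences, so power falls. With unequal sequences they do not fully cancel, and the realised estimate shifts. Neither consequence needs carry-over, so the washout does not prevent them.

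The trial plans about 20 analysed patients and little spare power, so avoidable variance in its single primary comparison matters. The standard crossover analysis removes it without extra data.

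**Working it through.** **Inputs from Section 11.4.** Effect: "We assume that the mean difference between drug and placebo will be a 15% lower seizure rate", that is 15 points. Spread: "the standard deviation of difference is 22" percent. The row "1 or 2 sided test" holds 2 in every column. Alpha is 0.05 and 20 completers are planned.

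**The plan's figure.** Exact noncentral-t power for a paired test, with noncentrality (15/22)√n and n − 1 degrees of freedom, is 0.778 at n = 18, 0.802 at n = 19 and 0.824 at n = 20. The stated 19 reproduces. The other three columns (21, 16 and 24) reproduce as well.

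**Time between periods.** The start of Period 2 lags the start of Period 1 by 12 + 4 = 16 to 16 + 6 = 22 weeks.

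**How likely is an unequal split?** The blocking and the dropout pattern are assumptions.

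| Assumption | Exactly 10/10 | 12/8 or worse | 13/7 or worse |
|---|---|---|---|
| Independent 50:50 draws; 10/10 is C(20,10)/2²⁰ | 18% | 50% | 26% |
| 15:15 randomised, a random 20 complete; 10/10 is C(15,10)²/C(30,20) | 30% | 25% | 5% |
| Blocks of 4, 20% dropout, first 20 completers (simulated) | 37% | 15% | 2% |

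**Effect of drift.** Let π be the change between periods. The mean difference is 15 + π in one sequence (n1 patients) and 15 − π in the other (n2 patients).

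- Bias of the pooled mean = π(n1 − n2)/N. At 12/8 this is 5 × 4/20 = 1 point for π = 5, and 10 × 4/20 = 2 points for π = 10.
- Approximate SD seen by the paired test = √(22² + π²[1 − ((n1 − n2)/N)²] × 20/19). At 10/10 with π = 10 this is √(484 + 105.3) = 24.3.
- The period-adjusted estimate is the mean of the two sequence-specific means. Its SE is (22/2)√(1/n1 + 1/n2) with 18 degrees of freedom, and it is free of π. At 10/10 the SE is 11 × √0.2 = 4.92 and power is 0.822. At 12/8 the SE is 11 × √0.2083 = 5.02 and power is 0.807.

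Simulated paired-test results, at least 100,000 runs per scenario, with 22 taken as the SD within a sequence:

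| Split | π | Bias (either way) | Paired power, adverse direction | Paired power, favourable direction | Paired type I error | Adjusted power |
|---|---|---|---|---|---|---|
| 10/10 | 0 | 0 | 82% | 82% | 5.0% | 82% |
| 10/10 | 5 | 0 | 81% | 81% | 4.6% | 82% |
| 10/10 | 10 | 0 | 76.5% | 76.5% | 3.2% | 82% |
| 10/10 | 15 | 0 | 69% | 69% | 1.8% | 82% |
| 12/8 | 5 | 1 | 75% | 86% | 4.9% | 81% |
| 12/8 | 10 | 2 | 64% | 87% | 4.6% | 81% |
| 12/8 | 15 | 3 | 47% | 86% | 4.0% | 81% |

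**Other reading of the SD.** If 22 is the SD over all patients and already includes a 10-point drift, the within-sequence SD is about √(484 − 100) = 19.6. Paired power is then about 85% at 10/10 and 73% at 12/8 in the adverse direction. Adjusted power is about 90% and 89%.

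**Cost with no drift.** At 10/10, power goes from 82.4% to 82.2%; at 12/8 to 80.7%; at 13/7 to 78.5%. That is about 0.2, 2 and 4 points.

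**The case against.** The strongest reply is that the problem is hypothetical and small. The documents give no period effect, and baseline antiepileptic drugs are held fixed throughout. The 15% improvement assumed on placebo is measured against baseline and says nothing about Period 2 differing from Period 1. Ten points of drift would be two thirds of the planned effect. At 5 points, power at 10/10 falls only from 82% to 81%. All of this stands, and it is why drift is shown as a range starting at zero.

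Section 11.4 calls 22 the standard deviation of the differences, which reads most directly as the SD over all patients. The loss from 82% to 76.5% against the plan's own figure depends on the other reading. This also stands, but the adjusted test does better under both.

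The balance sentence need not be a promise. The calculation gives an odd number, and rounding up to 20 so that 10/10 is possible is the natural sense. A reader might infer that the plan claims counting completers guarantees balance, but the text does not force that reading. The pharmacy schedule may also be blocked.

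It could be said that the analysis of variance in Section 11.1, or the comparison by randomised sequence in Section 11.42, already handles period. Neither does. The first is a pre-test with unspecified terms, whose only stated consequence concerns carry-over. The second defines who is analysed and as what; it puts no period term in the model.

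**Conclusion.** The plan leaves out a standard adjustment that costs almost nothing. With drift of 0 to 15 points (assumed), 20 completers and a within-sequence SD of 22, the paired test has between 82% and 69% power at 10/10, where the adjusted test has 82%. At 12/8, drift of 5 or 10 points shifts the estimate by 1 or 2 points and lowers paired power to 75% or 64% if the shift goes against the drug, where the adjusted test has 81%.

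Three stronger inferences are not supported. First, the drug estimate is not biased in general: at 10/10 there is no bias, and over randomisation the bias averages to zero if dropout is unrelated to sequence. It matters because only one realised split will be analysed. Second, the false-positive rate is not generally inflated. It stays at or below about 5% up to 12/8. It exceeds 5% at 13/7 (6.4% with 10 points of drift, about 7% with 15), a split with a chance of about 2% under blocks of four with 20% dropout, 5% if a random 20 of 15:15 complete, and 26% with no blocking. Third, the sample size is not wrong: 19 reproduces, and 20 completers keep at least 80% power with adjustment down to 12/8.

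This is a cheap improvement to the primary analysis, not a flaw that undermines the trial.

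**What to change.** In Section 11.1, replace the pooled paired t-test as the primary comparison with a period-adjusted crossover estimate. Either of these would do:

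- the equally weighted mean of the two sequence-specific active-minus-placebo differences, tested with N − 2 degrees of freedom; or
- a mixed model with treatment, period and sequence as fixed effects and patient as a random effect.

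The mixed model has a further advantage. Section 11.42 admits patients with data from only one period to the primary population, and neither the paired test nor the first option can use them.

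In Section 11.4, reword the balance sentence to say that 20 completers allow, but do not guarantee, equal sequences. Report completers by sequence.

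The cost is a few sentences and one degree of freedom, with no new patients or data. If there is no drift, the power given up is the 0.2 to 4 points shown in the working.

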#### 11.41 Independent period analysis

Based on calculations by the NINDS statistician, 24 completers would be needed in the event of detection of a carryover effect. If we detect a carryover effect, the additional sample size of 24 patients will have 80% power to detect a 45% decrease in seizure frequency in the PRX 00023 group, versus 15% in the placebo group, assuming the 25% common standard deviation.

Alpha = 0.050  
 Power = 0.800  
 Model = Two Sample t-test  
 Effect Size = 1.200  
 Pooled S.D. = 0.250  
 Mean(01) = 0.450  
 Mean(02) = 0.150

GROUP 1	GROUP 2	POWER
2	2	0.114
3	3	0.207
4	4	0.299
5	5	0.386
6	6	0.468
7	7	0.541
8	8	0.608
9	9	0.667
10	10	0.718
11	11	0.763
12	12	0.802

Total Sample Size = 24

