## 6. Subjects

### 6.1 Description of Study Population

The study will accrue up to thirty patients aged 18 to 65 inclusive with localization-related epilepsy with the goal of obtaining 20 completers, unless a carry-over effect is detected, in which case 24 completers would be required (see statistical analysis section 11. 4 and 11.41).

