#### 11.5 Accrual number request

In order to accrue 24 subjects, we are requesting a total potential sample size of 30. This should account for patients who do not have enough seizures to qualify during baseline, as well as dropouts.

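### The 24 completers called for if carry-over is found are sized for 30 points, twice the planned 15, without a stated reason, and the accrual statements in 6.1, 11.4, 11.41 and 11.5 need reconciling

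*Combined protocol and SAP*

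**What the plan says.** **Planned effect and primary target.** Section 11.4 sizes a paired t-test for a 15-point difference, "representing a 30% improvement on drug versus 15% improvement on placebo versus baseline", with an SD of within-patient differences of 22%. It obtains 19, rounds up for balance, and states that "we will accrue patients until 20 completers have been obtained". It then adds: "We request a total of 30 subjects to take into account a possible 20% dropouts".

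**Fallback.** Under section 11.1, a significant carry-over effect replaces the paired test with a two-group t-test in each period. Section 11.41 says that "24 completers would be needed in the event of detection of a carryover effect". Its second sentence describes the 24 patients as an additional sample and says that they "will have 80% power to detect a 45% decrease in seizure frequency in the PRX 00023 group, versus 15% in the placebo group", for a common SD of 25%. The supporting two-sample calculation gives 12 per group, power 0.802. Section 6.1 gives 20 completers as the goal, "unless a carry-over effect is detected, in which case 24 completers would be required", and refers to 11.4 and 11.41.

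**Accrual request.** Section 11.5 attaches no condition to the larger number: "In order to accrue 24 subjects, we are requesting a total potential sample size of 30". It continues: "This should account for patients who do not have enough seizures to qualify during baseline, as well as dropouts".

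**Timing.** Section 11.1 does not say when carry-over is tested. Section 16 says that data review is blinded and that no interim analysis is planned.

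**The concern.** A number described as needed or required will be read as the number that makes the fallback work for the effect the trial was planned on. Here it was obtained with a drug effect raised from 30% to 45%, with no explanation. If carry-over were declared, the team would recruit four more completers and could believe that the between-patient comparison was adequately powered for the planned effect.

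The completer target also governs the primary analysis, so it should read the same everywhere. As written, one section stops at 20, one gives 24, and two make 24 depend on a test result. If that result is to decide whether accrual continues, someone must compare outcomes by sequence while accrual is open. The plan gives no timing, significance level or masking for such a look.

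**Working it through.** **Method.** All power figures are for two-sided t-tests at 0.05, using the noncentral t distribution.
- Two-sample test: noncentrality = δ / (SD × √(2/n)), with 2n − 2 degrees of freedom and n per group.
- Paired test: noncentrality = δ × √n / SD of differences, with n − 1 degrees of freedom.

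**1. The plan's own figures.**
- Section 11.41: δ = 30, SD = 25, n = 12. Noncentrality = 1.2 / √(2/12) = 2.94, power 0.802. All 11 rows of the printed table reproduce.
- Section 11.4: δ = 15, SD of differences 22, 23, 20 and 25 give n = 19, 21, 16 and 24, as printed.

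Neither calculation is wrong for its inputs.

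**2. The fallback at the planned 15 points.** At SD 25, n = 12: noncentrality = 0.6 / √(2/12) = 1.47, power 0.290. With n = 10: 0.6 / √(2/10) = 1.34, power 0.246.

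The documents link no between-patient SD to the 15-point case, so a range is needed. The 25% is the value in 11.41. The low end, 15.6%, is 22/√2: the between-patient SD if the 22% SD of differences came from uncorrelated periods. The 30% is assumed.

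| SD | Power, 10 per group | Power, 12 per group | n per group for 80% | Difference giving 80% at 12 per group |
|---|---|---|---|---|
| 15.6% | 53% | 62% | 18 | 18.6 points |
| 22% | 30% | 36% | 35 | 26.3 points |
| 25% | 25% | 29% | 45 | 29.9 points |
| 30% | 18.5% | 22% | 64 | 35.9 points |

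No row reaches 80% with 12 per group, and each needs more than the 30 patients requested in total (36, 70, 90 and 128).

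**3. What these figures do not cover.** They are unconditional power for period 1.
- *Period 2.* If r points of drug effect persist in the drug-first group, the contrast shrinks to 15 − r. At SD 25 and 12 per group, r = 5, 10 or 15 gives 16%, 8% or 5%.
- *After a significant carry-over test.* Period 1 outcomes enter both the carry-over test and the period 1 test. The two are correlated, and an unconditional figure no longer applies.

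**4. The accrual statements side by side.**

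| Section | Completer target | What the 30 covers |
|---|---|---|
| 6.1 | 20, or 24 if carry-over is detected | ceiling, not broken down |
| 11.4 | 20, no condition | 20% dropout |
| 11.41, first sentence | 24 if carry-over is detected | not stated |
| 11.41, second sentence | an additional 24 (read literally, 20 + 24 = 44) | not stated; 44 exceeds 30 |
| 11.5 | 24, no condition | dropouts and baseline failures |

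At 20% dropout, 20/0.8 = 25 and 24/0.8 = 30. The 30 therefore matches a target of 24. From a target of 20, it allows a loss of 10/30 = 33%. With a target of 24, the dropout allowance uses all 30 places and leaves none for the baseline failures that 11.5 also counts.

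**5. What the target means for the primary test (15 points).**

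| SD of differences | 20 completers | 24 completers |
|---|---|---|
| 22% | 82% | 89% |
| 25% | 72% | 80% |

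**The case against.** *Section 11.41 hides nothing.* It states its inputs and never claims power for 15 points. A small pilot trial capped at 30 may size a fallback to what it can detect. This stands: a reader might infer a miscalculation or a false power claim, and the documents support neither. What remains is an unexplained change of effect, and wording that calls 24 needed when it serves only the larger effect.

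*Section 6.1 already reconciles the targets.* It gives one rule and points to 11.4 and 11.41, so 11.4 can be read as the base case and 11.41 as the exception. Section 11.5 speaks of a potential total. This stands in part, so it would go too far to say the sections wholly contradict each other. It does not resolve the unconditional 24 in 11.5, the additional 24 in 11.41, or the two accounts of what the 30 covers.

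*The clash with section 16 is an inference.* The sentence about interim analysis sits in the safety monitoring section, and no section schedules a carry-over test during accrual. That is fair. A reader might conclude that the plan breaks its own rule or unmasks treatment. The documents do not show this, and coded sequence labels could suffice. But a target cannot depend on a result that nobody has examined, so the trigger implies a look that section 16 does not provide for.

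*Carry-over is unlikely.* Section 11.1 says so. A half-life of 9.8 to 13.5 hours (section 4.42) against a washout of 4 to 6 weeks (section 7.54) gives at least 28 × 24 / 13.5 ≈ 50 half-lives. For pharmacokinetic carry-over this stands, and it limits the weight of the point.

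**Conclusion.** The point holds, with modest weight. The calculation in 11.41 is right for 30 points at SD 25%, but that effect is double the one in 11.4 and is not justified. For the planned 15 points, going from 20 to 24 completers raises unconditional period 1 power only from about 25% to 29% at SD 25%. Across SDs from 15.6% to 30%, power with 24 completers runs from 62% to 22%, so the conclusion does not depend on the SD chosen. The accrual statements agree in part and need alignment, and the trigger implies an outcome look that is not provided for.

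The results rest on a two-sided 0.05 t-test, equal groups and, for the central figure, the 25% SD of 11.41 applied to the 15-point difference of 11.4. The primary paired calculation is unaffected.

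**What to change.** - **Sections 6.1, 11.4, 11.41 and 11.5:** set one completer target in advance, within the 30 requested, and state it identically, together with what the 30 covers. Either 24 or 20 is workable, with the paired power shown above.
- **Sections 6.1 and 11.41:** remove the carry-over trigger for accrual, and delete the reference to an additional sample of 24 patients.
- **Section 11.1:** state that carry-over is tested only after the last completer. This then agrees with section 16.
- **Section 11.41:** state that the unconditional power of the period 1 comparison for 15 points at SD 25% is about 29% with 12 per group (25% with 10), and that 12 per group reaches 80% only at about 30 points. Do not claim these figures for period 2 or after a significant carry-over test. If the 45% stays as an input, give the reason for it.

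The cost is wording in five sections and no patients beyond the 30. The stated fallback power becomes less favourable. At 20% dropout, a target of 24 leaves no places for baseline failures. A target of 20 leaves 30 − 25 = 5, but gives only 72% paired power if the SD of differences is 25%.

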#### 11.42 Analysis populations

Intent To Treat (ITT)

The Intent-to-Treat (ITT) population includes all randomised subjects with at least one efficacy evaluation for at least one double-blind treatment period. The Safety Population consists of all subjects who administered at least one application of trial medication. The primary statistical analyses of efficacy will be performed on the ITT population and will compare the treatment groups on the basis of randomized treatment sequence regardless of the treatment actually received. All secondary efficacy analyses will be performed on the ITT population. Safety analyses will be performed on the safety population on the basis of treatment actually received where possible.

